#### 5.4.6 Anaphylaxis

Anaphylaxis is a serious allergic reaction that is rapid in onset and may cause death. Diagnostic criteria are outlined in Table 7.

**Table 7 Clinical Criteria for Diagnosing Anaphylaxis**

Anaphylaxis is highly likely when any one of the following 3 criteria are fulfilled:

1. Acute onset of an illness (minutes to several hours) with involvement of the skin, mucosal tissue, or both (e.g., generalized hives, pruritus or flushing, swollen lips/tongue/uvula) AND AT LEAST ONE OF THE FOLLOWING
 
 
a. Respiratory compromise (e.g., dyspnea, wheeze/bronchospasm, stridor, reduced peak expiratory flow (PEF), hypoxemia)
 
b. Reduced blood pressure or associated symptoms of end-organ dysfunction (e.g., hypotonia [collapse], syncope, incontinence)
 

2. Two or more of the following that occur rapidly after exposure to a likely allergen for that patient (minutes to several hours):
 
 
a. Involvement of the skin/mucosal tissue (e.g., generalized hives, itch/flush, swollen lips/tongue/uvula)
 
b. Respiratory compromise (e.g., dyspnea, wheeze/bronchospasm, stridor, reduced PEF, hypoxemia)
 
c. Reduced blood pressure or associated symptoms (e.g., hypotonia [collapse], syncope, incontinence)
 
d. Persistent gastrointestinal symptoms (e.g., crampy abdominal pain, vomiting)
 

3. Reduced blood pressure after exposure to known allergen for that patient (minutes to several hours):
 
 
a. Infants and children: low systolic blood pressure (age specific) or greater than 30% decrease in systolic blood pressure
 
b. Adults: systolic blood pressure of less than 90 mm Hg or greater than 30% decrease from that person’s baseline
 

As with the treatment of any critically ill patient, the treatment of anaphylaxis begins with a rapid assessment and maintenance of airway, breathing, and circulation. When a patient fulfills any of the 3 criteria of anaphylaxis outlined above, the patient should receive

epinephrine immediately because epinephrine is the treatment of choice in anaphylaxis. There undoubtedly will be patients who present with symptoms not yet fulfilling the criteria of anaphylaxis yet in whom it would be appropriate to initiate therapy with epinephrine, such as a patient with a history of near-fatal anaphylaxis to peanut who ingested peanut and within minutes is experiencing urticaria and generalized flushing. Subsequent interventions are determined on the basis of the clinical course and response to epinephrine.

Anaphylaxis should be reported in the eCRF as AE or SAE if it meets the seriousness criteria, with the event term “anaphylaxis”. The signs and symptoms of the anaphylaxis should be described in the appropriate part of the eCRF.

## **5.5 Pregnancy**

Any pregnancy in a female patient should be reported to the Sponsor from the time the patient signed the ICF until 12 months after the last infusion of study drug. Pregnancy reports should be submitted to the Sponsor within 24 hours of awareness of the pregnancy by the Investigator as per the reporting procedure outlined in the Site Manual.

Pregnancy occurring in the partner of a male patient participating in the study should be reported to the Investigator and the Sponsor following the same procedure for pregnancy in the female patient. The partner should be counseled, the risks of continuing the pregnancy discussed, as well as the possible effects on the fetus. Monitoring of the pregnant female should continue until conclusion of the pregnancy. The pregnant partner will need to sign an Authorization for “Use and Disclosure of Pregnancy Health Information” (a sort of specific consent form) to allow for follow-up of her pregnancy.

Although pregnancy is not an AE, all pregnancies must be followed until 6 to 8 weeks after the estimated date of delivery to determine their outcome. The pregnancy outcome will be notified to the Sponsor by submitting a follow-up pregnancy report form. If the outcome of the pregnancy meets the SAE criteria then the Investigator should report this case according to the SAE reporting process (Section 5.9).

## **5.6 Overdose**

An overdose of SAIT101 or MabThera® or Rituxan® is defined as an infusion of >1,000 mg during a single infusion in this study.

In case of overdose, the patient must be managed for any AE caused by overdose as per standard of care at the site or symptomatically and the case discussed with the Clinical Research Organization and Sponsor medical advisor for decision on treatment discontinuation of the patient.

When an overdose is reported during the course of the study, the patient should be monitored closely and evaluated by the Investigator to determine whether the patient experiences any AE or SAE as a result of the overdose.

Overdoses will be reported as protocol deviations. If the overdose is associated with an AE/SAE, the site should follow the AE/SAE reporting procedures described in Section 5 of this protocol and as per the eCRF completion guidelines.

## **5.7 Changes in Clinical Laboratory Assessment Results**

It is the responsibility of the Investigator or Sub-investigator to review the results of all laboratory tests as they become available. For each abnormal laboratory test result, the Investigator or Sub-investigator needs to ascertain if this is an abnormal (i.e., clinically significant) change from Baseline for that individual patient. This determination, however, does not necessarily need to be made the first time an abnormal value is observed. The Investigator or Sub-investigator may repeat the laboratory test or conduct additional tests to verify the results of the original clinical laboratory tests. If this laboratory value is determined by the Investigator or Sub-investigator to be a clinically significant change from Baseline for that patient, it is considered to be an AE.

## **5.8 Recording of Adverse Events**

### **Relationship**

The causal relationship of the study drug to all AEs occurring after the start of study drug infusion will be assessed as one of the following two categories.

1. Unrelated (AE for which relationship to the study drug can be ruled out). A reasonable possibility of the AE occurring is considered highly unlikely for one of the following reasons:
  - Occurrence of the event can be expected based on the patient's underlying disease, concurrent illness, or medical history.
  - Occurrence of the event can be expected based on the patient's age, gender, or other characteristics.
  - There is no apparent temporal relationship between study drug infusion and occurrence of the event. Example: Occurrence of an AE after a considerable length of time has elapsed since completion or discontinuation of study drug infusion.

- A causal relationship is considered highly unlikely from the status of study drug infusion and the course of the event. Example: An AE that recovers without treatment while continuing study drug infusion (excluding cases in which the patient becomes accustomed to the condition through continued study drug infusion).
  - The event is considered to be the effect of a concomitant drug.
  - The event is considered to be incidental (accident, incidental symptom, etc). Example: Occurrence of a femoral fracture resulting from a traffic accident.
  - A causal relationship of study drug infusion can be medically ruled out for some other reason.
2. Related (AE for which relationship to the study drug cannot be ruled out). A reasonable possibility of the AE occurring is considered likely for one of the following reasons:
- Occurrence of the event can be expected from the pharmacological or toxicological action of the study drug. Examples: Occurrence of pancytopenia when an effect on the hematopoietic system has been observed in non-clinical studies, or occurrence of dehydration with a study drug that has a diuretic action.
  - The same event was previously observed in non-clinical studies or clinical studies. Example: Occurrence of an event that was observed at a high incidence in Phase I studies.
  - A temporal relationship between study drug infusion and occurrence of the event is suspected. Example: Occurrence of allergic dermatitis several days after the start of study drug infusion.
  - A causal relationship is suspected from the outcome of the event following discontinuation or dose reduction of the study drug. Example: Rapid recovery of nausea following discontinuation of study drug infusion.
  - A causal relationship of study drug infusion cannot be medically ruled out for some other reason.

## Severity

AEs will be graded on a 3-point scale. The intensity of an adverse experience is defined as follows.

1 = Mild: Discomfort noticed, but no disruption to daily activity.

2 = Moderate: Discomfort sufficient to reduce or affect normal daily activity.

3 = Severe: Inability to work or perform normal daily activity.

## **5.9 Eliciting and Reporting Adverse Events**

After the patient has signed the ICF, but prior to initiation of study drug, only SAEs caused by a protocol-mandated procedure should be reported (e.g., SAEs related to invasive procedures such as biopsies). The Investigator or Sub-investigator will periodically assess patients for the occurrence of AEs and record AE information offered spontaneously by patients. To avoid bias in eliciting AEs, patients should be asked the following non-leading question: "How have you felt since your last visit?"

The QuintilesIMS must be notified of any SAEs within 24 hours of awareness according to the procedure outlined in the Site Manual.

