**Table 2 Schedule of Assessments**

	Screening a	Part A										Part B			EOS k	Un-Scheduled k
Week		Baseline b	0	1	2	2	4	8	12	16	20	24 j	26	36	52	
Visit	1	2	3	4	5	6	7	8	9	10	11	12	13	14	15	
Day (± window in days)	-30 (within -60) a	1	3	8	15 ±1	17 ±1	29 ±3	57 ±3	85 ±3	113 ±3	141 ±3	169 ±3	183 ±3	253 ±7	365 ±7	
Assessments																
Informed consent	X															
Inclusion/exclusion criteria	X	X c														
Demography	X															
Medical/surgical history	X															
Physical examination d	X	X	X	X	X	X	X	X	X	X	X	X	X	X	X	X
Neurological examination e	X	X	X	X	X	X	X	X	X	X	X	X	X	X	X	X
Vital signs f	X	X			X							X	X		X	X
Chest X-ray g	X															X s
Resting 12-ECG h	X														X	X
AEs/Serious AEs/ADRs		X	X	X	X	X	X	X	X	X	X	X	X	X	X	X
Prior/concomitant medication	X	X	X	X	X	X	X	X	X	X	X	X	X	X	X	X
Urine or serum pregnancy test i	X	X			X							X	X		X	X
Study drug																
Contact IXRS	X	X			X							X l	X l		X	
Randomization		X										X				
Drug infusion m		X			X							X	X			

	Screening a	Part A										Part B			EOS k	Un-Scheduled k
Week		Baseline b	0	1	2	2	4	8	12	16	20	24 i	26	36	52	
Visit	1	2	3	4	5	6	7	8	9	10	11	12	13	14	15	
Day (± window in days)	-30 (within -60) a	1	3	8	15 ±1	17 ±1	29 ±3	57 ±3	85 ±3	113 ±3	141 ±3	169 ±3	183 ±3	253 ±7	365 ±7	
Efficacy assessments																
HAQ-DI, including Patient's pain VAS n		X						X		X		X		X	X	
Patient Global Assessment VAS n		X						X		X		X		X	X	
Physician Global Assessment VAS		X						X		X		X		X	X	
Swollen and tender joint counts o		X						X		X		X		X	X	
Laboratory assessments																
Virology screening p	X	X					X	X	X	X	X	X		X	X	X
QuantiFERON ® -TB Gold q	X															X
IgG, IgM, IgA	X r							X		X		X		X	X	
CRP / ESR	X	X						X		X		X		X	X	
RF	X															X
Clinical chemistry, hematology and urinalysis	X	X			X		X	X	X	X	X	X		X	X	X
PK sampling s		X	X	X	X	X	X	X	X	X	X	X				X
PD (CD19+ B-cell) sampling s		X	X	X	X	X	X	X	X	X	X	X		X	X	X
Immunogenicity sampling t		X		X	X		X		X	X		X		X	X	

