## **6.6 Safety Analysis**

### **6.6.1 Adverse Events**

All reported terms for AEs will be coded using the Medical Dictionary for Regulatory Activities (MedDRA). No statistical testing will be performed for AEs. Adverse events will be summarized by the number and percentage of patients experiencing events by System Organ Class (SOC), Preferred Term (PT) and severity.

A listing of all ADRs will be presented. The listing will present SOC and PT of the ADR, severity, action taken, outcome, start and stop date of the ADR, study day of onset of the ADR, age, race, and gender.

The incidence of AESI in the study will be summarized in the similar way as ADRs.

A listing will be presented for all AEs with an outcome of death. Narratives will be prepared for all patients who died.

The incidence of all SAEs will be summarized by SOC and PT, if there are a sufficient number of SAEs to warrant such a presentation. A listing of all SAEs with an onset date prior to receiving study drug will also be presented. These listings will present SOC and PT of the SAE, severity, action taken, outcome, and relationship of the SAE to study drug, start and stop date of the SAE, study day of onset of the SAE, age, race, and gender.

Narratives will be prepared for all patients with a SAE, including deaths.

Narratives will be prepared for patients who permanently discontinued from study drug due to an AE.

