## 16.1. ADVERSE EVENTS

AEs will be coded using MedDRA 19.0 or higher.

For an AE change from non-serious AE to be a serious AE, it will be treated as a continuous event and count for once only in AE summary.

A treatment-emergent AE (TEAE) will be defined as any AE with an onset date on or after the date of first dose of study drug. AEs with increased severity during the treatment period will be considered as TEAEs whether already present during the pre-treatment period or not. Pre-existing AEs before the treatment period with no increase in severity during the treatment period will not be considered as TEAEs.

See [Appendix 1](#) for handling of partial dates for AEs. In the case where it is not possible to define an AE as treatment emergent or not, the AE will be classified by the worst case; i.e. treatment emergent.

For AE table summary, patients will be counted at most once for each Preferred Term (PT) and each System Organ Class (SOC).

All AEs will be listed.

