## APPENDIX 1. PARTIAL DATE CONVENTIONS

Imputed dates will NOT be presented in the listings. However, in general, when calculating relative days, partial dates with missing day only will be assumed to be earliest possible date for start date (i.e. 1st of the month) and latest possible date for stop date (i.e. 31st of the month); and partial dates with both missing day and month will be assumed to be 1st January for start date or 31st December for stop date

Algorithm for Treatment-Emergent Adverse Events:

START DATE	STOP DATE	ACTION
Known	Known	If start date < first IP taken date, then not TEAE If start date >= first IP taken date, then TEAE
	Partial	If start date < first IP taken date, then not TEAE If start date >= first IP taken date, then TEAE
	Missing	If start date < first IP taken date, then not TEAE If start date >= first IP taken date, then TEAE
Partial, but known components show that it cannot be on or after first IP taken date	Known	Not TEAE
	Partial	Not TEAE
	Missing	Not TEAE
Partial, could be on or after first IP taken date	Known	If stop date < first IP taken date, then not TEAE If stop date >= first IP taken date, then TEAE
	Partial	Impute stop date as latest possible date (i.e. last day of month if day unknown or 31st December if day and month are unknown), then: If stop date < first IP taken date, then not TEAE If stop date >= first IP taken date, then TEAE
	Missing	Assumed TEAE
Missing	Known	If stop date < first IP taken date, then not TEAE If stop date >= first IP taken date, then TEAE
	Partial	Impute stop date as latest possible date (i.e. last day of month if day unknown or 31st December if day and month are unknown), then: - If stop date < first IP taken date, then not TEAE

Document: \\eedc-vnasc01\Biosdata\Archigen\SAIT101\YWA21301\Biostatistics\Documentation\SAP  
 Author:

Version Number: V2.0  
 Version Date: 13Feb2019

Template No: CS\_TP\_BS016 Revision 4  
 Effective Date: 01Apr2016

Reference: CS\_WI\_BS005

START DATE	STOP DATE	ACTION
		- If stop date >= first IP taken date, then TEAE
	Missing	Assumed TEAE

Algorithm for Prior/Concomitant Medications:

START DATE	STOP DATE	ACTION
Known	Known	
	Partial	Impute stop date as latest possible date (i.e. last day of month if day unknown or 31st December if day and month are unknown)
	Missing	
Partial	Known	Impute start date as earliest possible date (i.e. first day of month if day unknown or 1st January if day and month are unknown)

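### SAP 16.1 counts a pre-existing AE that worsens on treatment as treatment-emergent, but the Appendix 1 algorithm goes by dates only and classes the same record as not treatment-emergent

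*Protocol*

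**What the plan says.** Three texts bear on this.

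- **Definition.** SAP section 16.1 first defines a TEAE as "any AE with an onset date on or after the date of first dose of study drug". It then widens the definition: "AEs with increased severity during the treatment period will be considered as TEAEs whether already present during the pre-treatment period or not". A further sentence excludes pre-existing events whose severity does not rise.
- **Algorithm.** SAP Appendix 1 gives a table for classifying AEs as treatment-emergent. Although the appendix is about partial dates, the table also has rows for complete dates. Where the start date is known, the rule is "If start date < first IP taken date, then not TEAE", whatever the stop date. Where the start date is described as "Partial, but known components show that it cannot be on or after first IP taken date", the result is again not TEAE for every stop date.
- **Collection.** Protocol section 5.9 says that, after consent, "prior to initiation of study drug, only SAEs caused by a protocol-mandated procedure should be reported". Protocol Table 2 marks the row "AEs/Serious AEs/ADRs" from the Baseline visit onward and not at Screening.

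**The concern.** The SAP states a rule for worsened pre-existing events and then supplies an algorithm that never applies it. Two programmers could each follow the SAP and produce different TEAE tables.

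The classification feeds nearly all the AE tables. SAP section 16.1 builds its summaries of severity, causality, drug discontinuation, drug interruption, serious events, deaths, drug reactions, events of special interest and immune-response events on TEAEs. A record classed as not treatment-emergent is absent from all of them. Worsening of a pre-existing problem after a B-cell-depleting infusion is something a safety table should show, and section 16.1 evidently means it to be shown.

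**Working it through.** No figure in the plan is in dispute, so the check sets the Appendix 1 table against the section 16.1 definition row by row. The table has 4 start-date states × 3 stop-date states (known, partial, missing) = 12 rows.

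| Start date | Rows | Appendix 1 result for an AE that began before first dose | Severity tested? |
|---|---|---|---|
| Known | 3 | Not TEAE, for any stop date | No |
| Partial, clearly before first dose | 3 | Not TEAE, for any stop date | No |
| Partial, could be on or after first dose | 3 | TEAE if the stop date (imputed to the latest possible date if partial) is on or after first dose, or is missing | No |
| Missing | 3 | Same as the row above | No |

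Severity is tested in 0 of 12 rows. In 3 + 3 = 6 rows an AE known to have begun before first dose is rejected. In the other 6 rows such an AE can still be accepted.

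Next, take a condition present before dosing that becomes more severe after it. The outcome depends on how the site records it.

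1. *One record, pre-dose start, severity raised later.* Section 16.1: TEAE. Appendix 1: not TEAE. The rules conflict.
2. *Worsening entered as a new AE dated at the worsening.* The start date is after first dose, so both rules give TEAE.
3. *Start date equal to the Day 1 dosing date.* Both rules give TEAE, because both include the date of first dose.

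Only case 1 is affected. The documents do not say in general which of cases 1 and 2 sites should follow. Protocol section 3.6.5.3 has worsened examination abnormalities recorded as AEs where appropriate, and section 5.7 makes a clinically significant laboratory change from Baseline an AE. Both point to case 2, but neither covers symptoms or clinical events generally. For an AE that turns serious, section 16.1 says "it will be treated as a continuous event and count for once only in AE summary". That leans towards a single record, but it is a counting rule and does not say which start date is kept.

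Section 16.1 also treats an AE as treatment-emergent when its status cannot be determined. That default does not help in case 1, because a known pre-dose start gives Appendix 1 a definite answer.

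**The case against.** The strongest reply is that almost no records can be affected. If section 5.9 of the protocol is followed, pre-dose events other than procedure-caused SAEs are not reported as AEs, and SAP section 10 shows that ongoing conditions are held on the Medical History page. Appendix 1 then has very little to reject, and worsening of a baseline condition would normally enter as a new AE after dosing. This stands and limits the size of the problem. It does not remove the conflict: procedure-caused SAEs that began before dosing are collected, and section 16.1 itself provides for pre-existing AEs.

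A second reply is that Appendix 1 is meant only for partial dates, so section 16.1 governs when dates are complete. The table does not read that way: its first three rows start from a known start date and the very first has both dates known.

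A third reply is that nothing disappears. Section 16.1 lists all AEs and all SAEs, and SAP section 16 makes no statistical comparison of safety between groups. This also stands. The issue is placement in the summary tables, and nothing in the documents suggests that it would differ between blinded arms.

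Some stronger readings are tempting but not supported.

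- A reader might infer that pre-dose events go unrecorded altogether. Procedure-caused SAEs are reported and ongoing conditions are captured as medical history.
- A reader might infer that Appendix 1 rejects every AE that began before dosing. Ambiguous and missing start dates can still be classed as TEAE.
- A reader might see a contradiction between section 5.9 and the promise in protocol section 6.6.1 that "A listing of all SAEs with an onset date prior to receiving study drug will also be presented". The listing can simply show whatever pre-dose SAEs were collected.

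**Conclusion.** The conflict is real and rests on the text alone. For an AE record with a start known to precede first dose and a later rise in severity, section 16.1 and Appendix 1 give opposite answers. Appendix 1 programmed as written drops the event from the TEAE-based summaries while leaving it in the listings.

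The practical effect is probably small. It needs a pre-dose record on the AE page, which section 5.9 makes uncommon, and it needs the worsening to be kept on that record. The documents give no rate for either, so no patient count can be derived; the lower bound is zero. The primary PK and main efficacy analyses are not touched. The point is worth correcting because a stated rule produces the wrong classification and the repair is minor. It does not show that worsening events are generally lost from the safety tables.

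**What to change.** 1. In SAP Appendix 1, change the six rows in which the start is known to precede first dose (known start dates, and partial dates that are clearly earlier). The result should be not TEAE unless severity increased on or after first dose, in which case TEAE. This matches section 16.1 and needs no further criterion.
2. State in the AE recording instructions, with a cross-reference in SAP section 16.1, that worsening after first dose of a condition present before dosing is entered as a new AE dated at the worsening. The documents do not say whether the AE page can hold more than one severity per record with dates. If it cannot, the severity exception could not be programmed from a single record, and this instruction is what makes the rule workable.

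The cost is one amended rule in the SAP table and one sentence of recording instruction. Counts would not be inflated, because section 16.1 counts each patient at most once per preferred term and system organ class. The change should be made before unblinding.
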